## **Statistical Analysis**

### Primary and Secondary Outcomes

The primary outcome in this trial is the change in A1C from baseline to six-months, with a priority secondary outcomes of change in A1C from six to twelve months, with the exposure of interest of TExT-MED+FANS.

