## **Hypothesis Analysis**

Initial changes in outcomes (primary and secondary) will be compared between groups with paired t-tests. This will be followed by a longitudinal method with a mixed effects regression model to account for correlated outcome data (zero-six month and six-twelve month changes) and loss to follow up. Analyses will be conducted by intent-to-treat, with participants analyzed according to their randomized intervention regardless of adherence.

Because change in A1C is the outcome, participants who drop out prior to six-months will not be included in the analysis. All participants who complete the twelve-month study will provide two outcome measures of six-month change: a zero-six month measure of treatment efficacy, and a six-twelve month measure of sustainability of treatment effect. The linear mixed effects model will include a random intercept term for participants. Fixed effects will include treatment allocation, initial level of A1C (zero month measure for treatment efficacy, six-month measure for sustainability), and a covariate of study period (zero-six month, six-twelve month). The main effect of treatment will test for group differences over both zero-six and six-twelve month periods. An interaction term of treatment by study period will test for differences in treatment effects by study period; treatment effects will be estimated and tested for differences by study period in this interaction model. Model assumptions including normality of model residuals and homogeneity of variance will be evaluated. A sensitivity analysis confined to adherent participants (those who have not opted out of messages and have received 75% or greater of messages confirmed by message delivery platform) will be conducted. Mixed effects linear regression models will be conducted on secondary outcomes as detailed above.

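### Adjusting the 6-12 month A1C change for the post-treatment 6-month A1C makes a maintained benefit look like further improvement, and a random intercept cannot carry any negative correlation left between the two changes

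*SAP*

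**What the plan says.** Under Primary and Secondary Outcomes, the SAP states: "The primary outcome in this trial is the change in A1C from baseline to six-months". The 6-12 month change is named there as a priority secondary outcome.

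Under Hypothesis Analysis, the model takes both changes as repeated outcomes: "All participants who complete the twelve-month study will provide two outcome measures of six-month change". It is chosen as a "mixed effects regression model to account for correlated outcome data (zero-six month and six-twelve month changes) and loss to follow up". The only within-patient structure given is this: "The linear mixed effects model will include a random intercept term for participants". No residual covariance, negative variance component or robust standard error is specified.

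The starting-level covariate is "initial level of A1C (zero month measure for treatment efficacy, six-month measure for sustainability"). Two treatment tests follow. For the pooled effect: "The main effect of treatment will test for group differences over both zero-six and six-twelve month periods". For the periods: "An interaction term of treatment by study period will test for differences in treatment effects by study period". Period-specific effects are taken from the interaction model. The planned assumption checks name residual normality and homogeneity of variance, but not within-patient correlation.

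**The concern.** There are two separate problems in one model.

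1. **The 6-month covariate.** The 6-month A1C is measured after randomisation, at the end of the messaging period, and is itself the primary endpoint value. Comparing arms at equal 6-month A1C is no longer the randomised comparison of 6-12 month change. At stake is the estimate that the SAP labels sustainability: an effect that is merely maintained would be read as one that is still growing.

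2. **The random intercept.** The two changes contain the 6-month value with opposite signs, which pushes their correlation downward. A conventional random intercept can represent only zero or positive correlation. If negative correlation remains after adjustment for starting level, the fitted variance goes to zero and the two rows are treated as independent. The pooled test is then conservative and the treatment-by-period test too liberal, and none of the named checks would reveal it.

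The same model is reused for the secondary outcomes and, under Planned Subgroup Analysis, for the moderators.

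**Working it through.** **Inputs.** From the SAP: the two outcomes, the covariates, the random intercept, and enrolment at A1C 8.5 or above. From the protocol (2.5): half of the supporters to each arm. The documents as published for review give no sample size, SD or A1C visit correlation, so there is no figure of the plan to reproduce. Assumed: SD 2 at each visit, visit correlation 0.5 to 0.7, either compound symmetry (CS) or first-order autoregressive (AR(1)), no dropout, two-sided 5% level. Simulations use 160 or 200 patients with baseline truncated at 8.5.

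**Part 1: the 6-month covariate**

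Let treatment lower A1C by d at 6 months, and let that benefit be held to 12 months.

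- True difference in 6-12 month change: (-d) - (-d) = 0.
- Difference between arms in the covariate (6-month A1C): -d.
- Slope of change on starting level, equal variances: b = -(1 - rho).
- Adjusted 6-12 month effect: 0 - b(-d) = bd = -(1 - rho)d.

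With d = 0.5:

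- rho = 0.5: -(0.5)(0.5) = -0.25
- rho = 0.7: -(0.3)(0.5) = -0.15

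Simulating the planned model gave -0.16 to -0.27. A second set of 1,500 trials gave -0.28 and -0.17 (CS 0.5 and 0.7) and -0.26 and -0.16 (AR(1) 0.5 and 0.7). The bias therefore does not depend on which correlation structure holds. The 0-6 month effect was recovered at -0.48 to -0.51 against a true -0.5.

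Consequences, weighting the periods equally:

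- Pooled effect: true (-0.5 + 0)/2 = -0.25. Model: about (-0.5 - 0.15)/2 = -0.33 to (-0.5 - 0.27)/2 = -0.39.
- Period difference: true 0 - (-0.5) = 0.50. Model: about -0.27 + 0.5 = 0.23 to -0.15 + 0.5 = 0.35.

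**Part 2: the random intercept**

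Correlation of the raw changes under CS: covariance proportional to rho - 1, each variance to 2(1 - rho), hence -0.5. Under AR(1) it is -(1 - rho)/2.

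The SAP adjusts each change for its starting level, so the residual correlation is what matters:

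- CS: r = -rho²/(1 + rho). At 0.5: -0.25/1.5 = -0.17. At 0.7: -0.49/1.7 = -0.29.
- AR(1): r = 0.

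If the rows are treated as independent, model SE / true SE is 1/√(1 + r) for the pooled effect and 1/√(1 - r) for the interaction:

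- CS 0.5: 1/√0.833 = 1.095 and 1/√1.167 = 0.926
- CS 0.7: 1/√0.712 = 1.185 and 1/√1.288 = 0.881

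Truncation at 8.5 weakens the residual correlation to -0.11 and -0.22. Simulated planned model, 160 patients, 2,000 trials:

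| Structure | Pooled SE, model / true | Pooled type I error | Interaction SE, model / true | Interaction type I error |
|---|---|---|---|---|
| CS 0.5 | 0.192/0.182 = 1.05 | 4.3% | 0.382/0.401 = 0.95 | 6.4% |
| CS 0.7 | 0.158/0.141 = 1.12 | 2.9% | 0.315/0.344 = 0.92 | 7.5% |

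The random-intercept variance was zero in 99-100% of these trials. With 200 patients (1,500 trials) the ratios were slightly milder: 1.04 and 1.09 pooled, 0.96 and 0.93 interaction. Under AR(1) 0.5 and 0.7 the 200-patient ratios were 0.97 to 0.99, with type I error 5.3-5.5% (pooled) and 5.7-6.4% (interaction). Simulation error on a type I rate is about 0.6 points.

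The 0-6 month contrast in the interaction model had an SE ratio of 0.97 to 1.00 and type I error of 4.5-6.1% across the truncated 200-patient scenarios. Allowing a negative within-patient correlation brought the pooled and interaction SE ratios to 0.99-1.00 under CS.

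**The case against.** **On the random intercept** the other side is strong. Sharing the 6-month value does not force a negative correlation. With equal variances the covariance of the raw changes is proportional to r(0,6) + r(6,12) - 1 - r(0,12); at 0.7, 0.7 and 0.3 this is +0.1. After adjustment, CS is the least favourable structure tried. With correlations 0.7/0.7/0.3, simulation of the planned model gave a fitted correlation of +0.31, a zero variance in 0% of runs, and type I error of 4.2% (pooled) and 5.4% (interaction). Software that permits a negative component would also remove the problem.

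A reader might therefore infer too much: that the random-intercept variance always collapses to zero, or that the standard errors are certainly wrong. The documents support neither, because they give no A1C correlations and the SAP already adjusts for starting level. What stands is that the SAP does not require a structure able to represent negative correlation and plans no check for it.

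In the unequal-correlation runs the 0-6 month contrast had type I error of 5.9-7.4%. The residual correlation there was positive, so this is not the negative-correlation problem. Unequal residual variance by period is the likely cause, and the SAP plans a homogeneity check.

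**On the 6-month covariate** one can say that conditioning on the 6-month level answers a legitimate question about later change among patients at equal A1C. That is a different quantity, no longer protected by randomisation, and the SAP presents the result as sustainability of the treatment effect. Correcting only the covariance would leave this covariate in place.

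**Conclusion.** The point holds in two parts of unequal certainty.

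- **Firm:** the model's 6-12 month treatment effect is not the between-arm difference in 6-12 month change. For a held benefit of 0.5 points the error is about -0.15 to -0.27, under both CS and AR(1) with correlations of 0.5 to 0.7. By the formula it scales with the 6-month benefit and shrinks as visit correlation rises. The pooled effect is overstated and the period difference understated.
- **Conditional:** under CS of 0.5 to 0.7 the pooled SE is about 5-12% too large (type I error about 3-4%) and the interaction SE about 4-8% too small (type I error about 6-7.5%). Under AR(1), or with a lower month 0 to month 12 correlation, both tests are near nominal.

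It would be wrong to conclude that the primary result is compromised. The 0-6 month estimate is not biased by the 6-month covariate, and its standard error is essentially unaffected by the negative-correlation problem. The plan should be changed for the priority secondary outcome, the pooled effect and the treatment-by-period test.

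**What to change.** Replace the model of successive changes with a model of A1C level at 6 and 12 months:

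- fixed effects: baseline A1C, visit, baseline-by-visit, treatment and treatment-by-visit;
- an unstructured within-patient covariance in place of the random intercept;
- the 6-month treatment contrast as primary and the 12-month contrast as secondary;
- the 6-12 month difference derived as the 12-month contrast minus the 6-month contrast.

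The only A1C covariate is then the pre-randomisation value, so a held benefit gives a 6-12 month difference of 0, and the covariance can take either sign. Because baseline is adjusted for, the 6-month contrast in level equals the contrast in change from baseline, so the primary outcome keeps its meaning. The same form should be carried to the secondary outcomes and moderator models.

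The cost is SAP wording, a few lines of code and one or two extra covariance parameters. No new data are needed. Robust standard errors or an unbounded compound-symmetric residual would address only the second problem.

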#### Secondary Objectives:

1. Examine the change in percent glycosylated hemoglobin at 12 months for FANS supported patients vs non-augmented support patients.
2. Examine changes in psychosocial and behavioral outcomes at 6 and 12 months for FANS supported patients vs non-augmented support patients.

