### **Planned Subgroup Analysis:**

To determine if subgroups of participants are differentially affected by the intervention, secondary analyses evaluating intervention moderators are planned. For A1C and each of the secondary outcomes, interaction terms (randomized intervention-by-moderator product terms) will be added to the mixed effects linear models described above. Variables evaluated as moderators will include gender, language preference, years with diabetes, baseline frequency of mobile usage, physical proximity to supporter, baseline social connectedness, and baseline support. If any of these factors indicate significant moderation, intervention effects will be estimated by levels of the moderator. Secondary analyses of the primary A1C outcome will use structural equation modeling to evaluate the secondary behavior and efficacy outcomes as mediators of the TEXT-MED+FANS intervention. Initial analyses will evaluate the associations of changes in behavior and efficacy variables with change in A1C using mixed effects models as detailed above. The A1C mediating model will then include randomized intervention, baseline A1C, any moderating variables detected above, and change in a behavior or efficacy outcome as a possible mediator. Mediation will be tested with bootstrapped samples, evaluating the direct and indirect (mediated) effects of changes in behavior and efficacy outcomes. The final model will include significant moderators and mediators of the TEXT-MED+FANS effect on A1C.

Additionally, after completion of enrollment, substantial differences in baseline support and contact between patients and their selected supporters became evident, as some supporters took up to three weeks to enroll. We now plan on conducting a sub-analysis based on

supporter immediate availability for enrollment versus delayed enrollment.

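### The adjusted 6–12 month A1C estimate conditions on six-month A1C, a post-randomisation value, and the SAP names no confirmatory test for the six-month primary outcome

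*SAP*

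**What the plan says.** **Outcomes.** Under Primary and Secondary Outcomes the SAP states: "The primary outcome in this trial is the change in A1C from baseline to six-months". It adds "priority secondary outcomes of change in A1C from six to twelve months". The first item under Secondary Objectives is worded differently: "Examine the change in percent glycosylated hemoglobin at 12 months for FANS supported patients vs non-augmented support patients".

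**Analysis (SAP, Hypothesis Analysis).** Changes in primary and secondary outcomes are first compared between groups by t-tests, which the SAP calls paired. A random-intercept mixed model follows, in which each completer contributes two changes: 0–6 months (efficacy) and 6–12 months (labelled sustainability of the treatment effect). The fixed effects are treatment, "initial level of A1C (zero month measure for treatment efficacy, six-month measure for sustainability), and a covariate of study period". Two treatment tests come from this model:
- Without the interaction: "The main effect of treatment will test for group differences over both zero-six and six-twelve month periods".
- With treatment by period: "treatment effects will be estimated and tested for differences by study period in this interaction model".

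The approach extends to the other endpoints: "Mixed effects linear regression models will be conducted on secondary outcomes as detailed above".

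**Timing.** Dyads are randomised once the supporter has enrolled (SAP, Enrollment & Randomization; Protocol 2.6), so six-month A1C is a post-randomisation measurement.

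**Not stated in the text available.** There is no sample size, SD, target effect, significance level or ranking of tests. The Protocol is a screening and enrolment manual without analysis content.

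**The concern.** Six-month A1C, together with baseline, defines the primary outcome. Holding it fixed in the 6–12 rows compares patients from the two arms who reached the same six-month value, and that is no longer a randomised comparison. If the intervention lowered A1C by month 6, the matched control patients are those who did unusually well without it. They tend to drift back upwards, and the drift is credited to the intervention as continuing benefit.

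The coefficient that the SAP labels sustainability can therefore suggest further gain when the arms merely ran in parallel, and can sit near zero when half the benefit has gone. The same model is planned for the secondary outcomes and carries the moderator analyses in Planned Subgroup Analysis.

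Separately, the SAP offers several tests that could be reported for the primary outcome and ranks none, so the primary p-value could be chosen after the results are known.

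**Working it through.** **Inputs.** The model and covariates are from SAP, Hypothesis Analysis. All sizes are assumptions: 75 per arm, SD 2, baseline truncated at the 8.5 entry limit, no dropout, two-sided 0.05, ρ from 0.4 to 0.7, d6 = −0.8 (also −0.5). There is no stated figure to reproduce.

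**1. What the adjusted 6–12 coefficient estimates.** With equal visit SDs, the slope of the 6–12 change on six-month A1C is ρ − 1. The adjusted arm effect is

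(d12 − d6) − (ρ − 1)·d6 = d12 − ρ·d6.

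The 12-month effect is d12, and the difference in 6–12 change is d12 − d6. The coefficient equals the first only if ρ·d6 = 0, and the second only if ρ = 1 or d6 = 0.

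**2. Numbers for d6 = −0.8.**

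| Scenario | d12 | True d12 − d6 | Formula, ρ = 0.4 | Formula, ρ = 0.7 | Simulated SAP model |
|---|---|---|---|---|---|
| Sustained | −0.8 | 0 | −0.80 + 0.32 = −0.48 | −0.80 + 0.56 = −0.24 | −0.52 to −0.26 |
| Half lost | −0.4 | +0.40 | −0.40 + 0.32 = −0.08 | −0.40 + 0.56 = +0.16 | −0.12 to +0.15 |
| All lost | 0 | +0.80 | +0.32 | +0.56 | +0.29 to +0.54 |

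The simulation fitted the stacked random-intercept model by REML under compound-symmetric and AR(1) correlation (600 trials per scenario, with a second run of 1,500). The fitted slope on initial A1C was −0.63 at ρ = 0.4 and −0.31 to −0.34 at ρ = 0.7, so slope + 1 is close to ρ, as the formula needs. With d6 = −0.5 the coefficient was −0.16 to −0.31 if sustained and −0.06 to +0.09 if half was lost. A large-sample fit (200,000 patients, SD 1.8, d6 = −0.5, sustained) gave about −0.35, −0.25, −0.15 and −0.10 at ρ = 0.3, 0.5, 0.7 and 0.8, which matches −0.5 × (1 − ρ).

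**3. How often this misleads.** For an exactly sustained effect of −0.8, the model declared further benefit (p < 0.05) in about 19–40% of trials. A hand check uses SE ≈ 2·√(1 − ρ²)·√(2/75):
- ρ = 0.4: SE 0.299, z = 0.48/0.299 = 1.60, rate about 36%.
- ρ = 0.7: SE 0.233, z = 0.24/0.233 = 1.03, rate about 18%.

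With d6 = −0.5 the rate was 11–18%. A half loss from −0.8 was flagged in 1–9% of trials, against 19–37% for the 6–12 change adjusted for baseline only.

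**4. The primary outcome.** The interaction model's 0–6 contrast uses baseline A1C only. It came out at −0.78 to −0.82 for a true −0.8, with power 74–94%, the same as six-month ANCOVA. The pooled main effect is a different quantity: −0.53 to −0.66 (sustained), −0.35 to −0.47 (half lost), −0.13 to −0.26 (all lost). Under the null, with the t-test run between arms, the individual rejection rates were 4.3–5.0% (t-test), 3.9–5.3% (0–6 contrast) and 2.6–5.0% (pooled). Free choice between the two tests that target 0–6 gave 5.9–7.1%; counting the pooled test as well gave 7.5–10.1%.

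**5. The 12-month secondary.** Take d6 = d12 = −0.8. Measured from baseline, the 12-month arm difference is −0.8. Measured from month six it is −0.8 − (−0.8) = 0. The two descriptions of this outcome would give opposite headlines for the same data.

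**The case against.** The strongest reply is that the SAP already plans an unadjusted between-group comparison of 6–12 changes, which correctly targets d12 − d6. This stands. In a repeat at the same settings that comparison detected a half loss in about 21–38% of trials, as often as the proposed analysis, so the fix brings no power gain over it. What remains is that the plan holds two durability estimates that can disagree, ranks neither, and attaches the sustainability label to the misleading one.

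A second reply is that change given the six-month level is a legitimate question. It is, but it is not a randomised comparison and it does not measure whether the effect lasted.

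Third, the sizes are assumed. This also stands. Both arms receive the same patient programme, so −0.8 would be an increment over an active control, and no document supports it. The false further-benefit rate moves with sample size: about 13–25% at 50 per arm and 31–67% at 150. With 75 per arm and d6 = −0.3 it falls to about 6–9%, against 2.5% nominal in that direction. With no six-month effect the distortion is zero.

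Fourth, the error inflation from the unnamed primary test is modest, and reporting the pooled effect as the six-month result would contradict the SAP's own outcome definition. Agreed.

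Fifth, the secondary objective gives no starting point, so it may be only ambiguous. However, it parallels the six-month primary objective, which the SAP defines from baseline, so a baseline-to-12-month reading is the natural one.

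**Conclusion.** The concern holds and should be fixed. The mechanism and its direction follow from the SAP text alone: whenever there is a six-month effect and ρ is below 1, the adjusted 6–12 coefficient is shifted by (1 − ρ)·d6 towards apparent continuing benefit. At d6 = −0.8 and ρ 0.4–0.7 that shift is −0.24 to −0.48 A1C points by the formula. The percentages in the working are illustrative, since they rest on an assumed sample size, SD and effect.

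The primary six-month effect is not biased and can be read from the planned interaction model. The missing confirmatory label and the two descriptions of the 12-month outcome would each be minor alone, but they sit in the same paragraphs and are settled by the same edit.

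**What to change.** 1. **Primary test.** Name one: the 0–6 month treatment contrast adjusted for baseline A1C. Label the t-test (as a two-sample test; a paired test cannot compare arms) and the pooled main effect as supportive.
2. **Durability.** Remove six-month A1C as a covariate. One model can serve both purposes: A1C at months 6 and 12 as repeated measures, with arm, visit, arm by visit and baseline A1C, in the patients the SAP already includes. Adjusted for baseline, its month-6 contrast is the 0–6 change contrast. Its month-12 contrast is the 12-month effect, and the second minus the first is durability. Apply the same rule to the secondary outcomes.
3. **Key secondary.** Reconcile Secondary Objectives with Primary and Secondary Outcomes, and state whether the quantity is the change from baseline to month 12 or from month 6 to month 12.

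**Cost.** SAP wording and model code, with the same data and the same analysed patients. The pooled test is given up as a possible primary test. At ρ = 0.4 with a fully sustained effect of −0.8 it has more power (86–88% against 76–79%). The SAP was written at least in part "after completion of enrollment, substantial differences in baseline support and contact" became evident, so the change should be dated, justified and made before arm-level results are seen.

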**Patient recruitment**

Patients were recruited from July 2017 to October 2018. IRB approval for this study was obtained prior to study initiation from the USC Health Sciences Institutional Review Board. This study enrolled ED patients with both type I and type II diabetes at LAC+USC (Los Angeles County + University of Southern California Medical Center). ED patients with diabetes in this healthcare system have been found to have poor glycemic control, poor diabetes specific knowledge, and poor access to primary care.

Screening, Eligibility Criteria and Recruitment

Table 1: Eligibility criteria for participants

Exclusion Criteria
Psychiatric involuntary hold, or in police custody
Altered mental status
Clinically unstable to consent and complete baseline assessment
Inclusion Criteria
Age 18 or greater

Stable ownership of mobile phone
Able to send and receive text messages
Reads English or Spanish
A1C 8.5 or greater
Identifies a support person who can be contacted within 2 weeks to enroll

Trained research assistants (RA) conducted screening and enrollment during the daytime and evening hours in the LAC+USC ED. They surveyed the ED electronic patient tracking system for patients with diabetes. Inclusion and exclusion criteria are listed in Table 1. Only subjects with A1C  $\geq 8.5\%$  were enrolled in this trial, as these patients have the greatest need for intervention and potential to demonstrate beneficial intervention effect. The A1C-based eligibility requirement was verified in the emergency department during the patient's visit, using the Afinion AS-100 capillary point-of-care A1C meter (Axis-Shield PoC AS, Oslo, Norway). Patients who reported both type 1 and 2 diabetes were enrolled, as prior work with this population has shown that 30% of patients are unsure which type of diabetes they have. RAs explained the purpose of the study and obtained written informed consent in the language of the patient's preference. To be eligible, patients had to identify a family member or friend to agree to serve as a supporter. Patients were aware at enrollment that the designated supporter could receive multiple text-messages per day, and would be prompted to offer increased support.

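### The standard error of the primary 0-6 month A1C contrast is pooled with 6-12 month residuals, so its test is miscalibrated if variability differs between the two periods

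*SAP*

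**What the plan says.** The SAP, under Primary and Secondary Outcomes, states: "The primary outcome in this trial is the change in A1C from baseline to six-months". Under Hypothesis Analysis, changes are first compared between groups by a t-test, and a longitudinal model follows. For that model, "All participants who complete the twelve-month study will provide two outcome measures of six-month change", and "The linear mixed effects model will include a random intercept term for participants". The fixed effects are treatment, study period and one starting-value covariate: "initial level of A1C (zero month measure for treatment efficacy, six-month measure for sustainability".

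The only interaction with period is treatment: "An interaction term of treatment by study period will test for differences in treatment effects by study period". The period-specific effects come from that fit: "treatment effects will be estimated and tested for differences by study period in this interaction model". No starting-A1C-by-period term and no period-specific residual variance is named. On diagnostics the SAP says: "Model assumptions including normality of model residuals and homogeneity of variance will be evaluated". It names no action if a check fails. The same model form is reused for the secondary outcomes.

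**The concern.** The two periods need not be equally variable. Under Protocol 2.4.4 the text messages run for six months only, so the first change is measured on messages and the second after they stop. The SAP itself treats the first as efficacy and the second as sustainability.

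A model with one residual variance averages the scatter of both periods and uses the average to set the standard error of each. If 0-6 month changes are noisier than 6-12 month changes, the primary standard error is too small and false positives exceed the nominal level. If they are less noisy, the interval is too wide and power is lost. Either way, the primary p-value and interval would depend on how variable A1C is in a period that is not part of the primary outcome.

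**Working it through.** **Inputs.** From the documents: two changes per completer, random intercept, one starting-A1C slope, treatment by period (SAP, Hypothesis Analysis); eligibility limit "A1C 8.5 or greater" (SAP, Table 1); half of supporters per arm (Protocol 2.5). The documents give no sample size, SD, slope or dropout rate, so there is no stated figure to reproduce and every size below rests on assumed values. Slopes are for change on starting A1C (a slope of later on earlier A1C of 0.5 is -0.5 here).

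**Step 1: is the estimate biased?** With complete data and treatment by period in the model,

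0-6 contrast = difference in mean 0-6 change - b × difference in mean zero-month A1C,

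where b is the shared slope. Randomisation makes the last difference zero on average, so the contrast is centred correctly whatever b is. In the simulations of step 4, with a true effect of 0 or 0.6 points, bias was -0.015 to +0.009 A1C points.

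**Step 2: does the shared slope cost precision?** Relative to the period's own slope b1, variance is inflated by about 1 + (b - b1)² × SD(baseline)² / SD(residual)². In one simulated case b averaged -0.866 against a true -0.7, with baseline SD about 1.6 and residual SD 2.0: 0.166² × 1.6² / 2.0² = 0.018, or about 2%.

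**Step 3: what does pooling the residual variance do?** Let q = residual SD (6-12) / residual SD (0-6). With equal numbers in each period and no random-intercept variance,

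model SE / true SE = sqrt((1 + q²)/2), and type I error = 2 × [1 - Φ(1.96 × ratio)].

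| q | SE ratio | Type I error |
|---|---|---|
| 0.7 | 0.863 | 9.1% |
| 0.8 | 0.906 | 7.6% |
| 0.9 | 0.951 | 6.2% |
| 1.0 | 1.000 | 5.0% |
| 1.1 | 1.051 | 3.9% |
| 1.25 | 1.132 | 2.7% |

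**Step 4: simulation of the SAP interaction model (REML).** 150 patients 1:1, baseline at least 8.5 with mean about 10.7, 15% missing at month 12, no treatment effect, 1,500 runs per row (Monte Carlo SE about 0.6 points). ANCOVA is 0-6 change on treatment and zero-month A1C.

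| Slopes 0-6 / 6-12 | Residual SD 0-6 / 6-12 | Model SE v empirical SE | Ratio | Type I, SAP model | Type I, ANCOVA |
|---|---|---|---|---|---|
| -0.5 / -0.5 | 1.8 / 1.8 | 0.294 v 0.292 | 1.01 | 5.3% | 4.6% |
| -0.7 / -0.3 | 1.8 / 1.8 | 0.304 v 0.295 | 1.03 | 4.7% | 5.3% |
| -0.9 / -0.2 | 1.8 / 1.8 | 0.317 v 0.291 | 1.09 | 3.2% | 4.5% |
| -0.7 / -0.3 | 1.8 / 1.5 | 0.289 v 0.301 | 0.96 | 5.7% | 5.3% |
| -0.7 / -0.3 | 2.0 / 1.4 | 0.316 v 0.330 | 0.96 | 6.1% | 5.1% |
| -0.5 / -0.3 | 1.8 / 1.2 | 0.272 v 0.300 | 0.91 | 7.4% | 5.1% |
| -0.5 / -0.5 | 2.0 / 1.4 | 0.290 v 0.327 | 0.89 | 7.9% | 4.1% |
| -0.7 / -0.3 | 1.5 / 1.8 | 0.275 v 0.250 | 1.10 | 2.9% | 4.8% |

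The 2.0 / 1.4 row with equal slopes agrees with step 3 once dropout is counted: pooled variance = (150 × 4.00 + 127.5 × 1.96) / 277.5 = 3.06, and sqrt(3.06 / 4.00) = 0.875, against 0.89 simulated.

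A second set with 160 patients and 6,000 runs gave SE ratios of 0.89-0.97 and errors of 6.0-8.0% when the 0-6 SD was larger. With SDs 1.6 / 2.0 the ratio was 1.15 and the error 2.5%. In that case power was 71% for an effect that ANCOVA detects with 80%. By hand: Φ(1.96 + 0.84 - 1.15 × 1.96) = Φ(0.55) = 0.71.

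**Step 5: which component is responsible?** With 160 patients and 1,200 runs, adding only a starting-A1C-by-period term moved the error from 7.6% to 7.0% (SDs 2.0 / 1.5), from 8.3% to 7.5% (1.8 / 1.2) and from 2.6% to 2.7% (1.6 / 2.0). Freeing only the residual variance gave 4.6-5.0%. Doing both (3,000 runs, SDs 2.0 / 1.4, 1.8 / 1.2 and 1.6 / 2.0) gave 4.2-4.6%, with SE ratios of 1.01-1.04. With equal slopes and variances, doing both made no practical difference (5.0% v 4.9%).

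**The case against.** **The SAP never states a single residual variance, and it will check homogeneity.** Both are true. The single variance is inferred from a random-intercept model with homogeneity listed as an assumption. The check is the right diagnostic, but with no stated response any repair would be chosen after the data are seen.

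**The initial t-test on the 0-6 change is untouched.** It uses neither a shared slope nor a variance pooled across periods. However, it is labelled paired although it compares two groups, and the SAP does not say whether it or the model decides the primary outcome. It is not a settled fallback.

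**Nothing shows that the variances differ.** This stands. No SD is given for either period, and stopping the messages makes a difference plausible without showing it. With A1C equally correlated across visits and the eligibility cut as the only asymmetry, the simulated error was 5.3-5.8%.

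Three stronger readings are tempting and not supported:

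- *The primary estimate is biased.* Step 1 shows that it is not.
- *The shared slope is the main fault, as an average of the two period slopes dominated by month-6 A1C.* The fitted slope can be steeper than both true slopes (-0.87 against -0.7 and -0.3). With equal SDs it did little harm unless the slopes were far apart, and then the test was conservative (3.2%).
- *The 8.5 cut-off shows that the periods have unequal variance.* It narrows the spread of the baseline covariate and says nothing about residual scatter around the regression.

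**Conclusion.** The point holds for the standard error, p-value and interval of the 0-6 contrast. Under assumed inputs of 150-160 patients, type I error is roughly 6-8% when the 0-6 residual SD is clearly larger and roughly 2-3% when it is smaller. In the smaller-SD case simulated for power, power fell from 80% to 71%. The idealised formula reaches 9.1% at an SD ratio of 0.7. With equal SDs the effect is generally negligible.

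A reader might infer that the primary test is anti-conservative. The documents do not support a direction, because they give no SDs for either period. The case for changing the plan is that protection is nearly free, not that an error is known to have occurred.

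**What to change.** In the SAP, Hypothesis Analysis, do one of the following:

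- State that the 0-6 month contrast is estimated and tested by regressing 0-6 change on treatment and zero-month A1C.
- Keep the stacked model, let the residual variance differ by period and add a starting-A1C-by-period term.

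Name the chosen analysis as the one that decides the primary outcome, and use the same form for the secondary outcomes. The cost is one sentence, plus two extra parameters if the stacked model is kept. No new data or patients are needed, and in the simulations nothing was lost when the periods were alike.
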